The primary outcome model will be a hierarchical mixed model (i.e., GLMM) that will include time (categorical; baseline, mid-point, and end-of-treatment), treatment (app-CBT vs. supportive attentional control), and their interaction as fixed effects, and will model time as a repeated measure using either an autoregressive (AR1), Toeplitz, compound symmetry, or unstructured covariance matrix, based on best fit determined by AIC and BIC. The unstructured covariance matrix model will only be used if this model fits significantly better than alternative simpler models, based on -2 log likelihoods. The main hypothesis test will be based on a specific contrast of treatment difference at week 12. Because these analyses will include all subjects who are randomized and complete at least one assessment, it is an intent-to-treat analysis. These analyses will include only the 3 assessments from baseline to post-treatment and will not include the 3-month or 12-month follow-up (FU) assessments, because treatment response could be affected by subjects seeking other treatments during the FU period. Between-group effect sizes will be calculated using Cohen's *d*. This analysis will then be repeated using the per-protocol sample.

In addition to the analyses specified above, we will describe the proportion of subjects in each treatment arm who achieve response, where response is defined as a 25% or greater reduction in Y-BOCS score from baseline to end of treatment (week 12) (Storch et al., 2006). While no formal comparisons will be made between treatments, the reporting of response rates is clinically useful and will facilitate comparison to other studies in the field. We will report response as observed (excluding subjects with missing data at week 12) and will additionally examine how rates may change when a) applying a last observation carried forward approach, and b) conservatively considering subjects with missing week 12 scores as non-responders.

Secondary endpoint: Difference in secondary clinical outcomes (i.e., QIDS-SR, WSAS, Q-LES-Q-SF) at the end of treatment (i.e., preliminary efficacy for secondary symptoms)

Analysis:

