We will use hierarchical mixed models similar to the ones used for the primary and secondary outcome analyses, but will add follow-up assessments (i.e., 3-month and 12-month) to the data as additional time-points. We will then use specific contrasts (for each outcome model) to test for significant treatment group differences at the 12-month follow-up time-point. In the case that at least 10% of the participants who completed the end-of-treatment assessment initiated additional or subsequent evidence-based treatment for OCD at clinically relevant dosage (for medication) or frequency (for therapy), we will conduct a sensitivity analysis for this aim using treatment (yes/no) as a time-varying covariate in the model to account for the potential effect of outside treatment. In this context, ‘evidence-based’ treatments will be operationally defined to include any psychosocial or medication treatments indicated for OCD or closely related anxiety disorders that have shown efficacy in prior clinical trials, and ‘clinically relevant dosage’ will be evaluated by psychiatrists or psychologists in our treatment program who specialize in OCD or related disorders. In addition, we will also add descriptive stats about how many participants are responders at both end-of-treatment and 12-month follow-up, how many participants are new responders by the 12-month follow-up, how many participants are no longer considered responders at the 12-month follow-up, and how many participants were not considered responders at either assessment. No formal comparisons will be made between treatments in these numbers.

Exploratory endpoint 3: Treatment utilization for OCD concerns following the 3-month follow-up.

Analysis:

We will use logistic regression analysis to examine whether the likelihood of seeking further treatment for OCD during the treatment or follow-up phases (overall, combined) differs between participants who were assigned to the app-CBT and those assigned to the supportive attentional control condition. For this analysis, we will operationally define “treatment utilization” as any indication of participants seeking treatment for OCD during or following the treatment phase, regardless of whether the treatments sought are pharmacological or therapy-based, at sufficient or insufficient dosage/frequency, or considered evidence-based or not.

D. Power analysis

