The sample size required to test a significant treatment response difference between the app-CBT and the control condition at the end of treatment is n=116 (n=58 per group). The sample size estimate is based on a single degree of freedom contrast in an ANOVA design, implemented in SAS for Windows version 9.4. The power model used a two-sided alpha=0.05, a power of 0.90, equal allocation of participants into both treatment arms, an assumption of an effect size of 0.76 comparing the two treatments at the end of treatment, as well as an assumption of a standard deviation of 1.1. The anticipated effect size of the app-CBT was conservatively based on the 95% lower confidence limit of the mean between-group effect size of CBT vs. psychological placebos reported in Ost et al. (g=1.29, 95% CI: [0.76–1.81]; Öst, Havnen, Hansen, & Kvale, 2015). We chose this conservative limit, because the effect sizes of recent, large RCTs of CBT or iCBT vs. various psychological control conditions have been quite variable, ranging from a high of d=1.12 in a comparison of iCBT against online non-directive supportive therapy (n=101; E.

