Andersson et al., 2012) to $d=0.55$ in a trial of iCBT vs. internet-based progressive relaxation therapy (n=179; Kyrios et al., 2018) and $d=0.52$ in a trial of CBT vs. stress management training (n=73; Whittal, Woody, McLean, Rachman, & Robichaud, 2010). In the process of evaluating effect sizes from previous trials, we did not differentiate between internet-delivered CBT and face-to-face CBT, because a meta-analysis including 13 RCTs that directly compared these two treatment modalities in patients with various psychiatric and somatic conditions (total N=1053) showed a pooled effect size (Hedges' g) at post-treatment of -0.01 (95% CI: -0.13 to 0.12; G. Andersson, Cuijpers, Carlbring, Riper, & Hedman, 2014); of note, though, this direct comparison has not been done in trials with patients with OCD. Furthermore, in the wake of the COVID-19 pandemic, various negative mental health states and stressors – including anxiety, worry, depression, loneliness, financial strain, and trauma symptoms – have increased in the US population (e.g., Fowers & Wan, 2020). The variability of these negative mental health states and stressors will likely be higher than during non-pandemic times as multiple waves of the pandemic and state-wide measures of social interaction restrictions sweep the nation in the foreseeable future. In response, we used a standard deviation of 1.1 (instead of the standardized 1.0) in our power calculations to allow for a 10% increase in the variability of symptom severity estimates during the ongoing effects of the COVID-19 pandemic and its socioeconomic aftermath. Lastly, we assumed a conservative drop-out rate of 20% by end of treatment, based on the dropout numbers reported in a meta-analysis of 18 studies targeting self-help treatments for OCD, where studies with self-administered treatment without therapist contact had a drop-out rate of approximately 40%, compared to drop-out rates of 17-20% in treatments with minimal to low therapist contact (Pearcy, Anderson, Egan, & Rees, 2016); the meta-analysis by Ost et al. (2015) reported an estimated dropout rate of 15.5% from in-person CBT treatment.

VII. RISKS AND DISCOMFORTS

A. Complications of surgical and non-surgical procedures

Not applicable

B. Drug side effects and toxicities

Not applicable

C. Device complications/malfunctions

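### The covariance structure of the primary model is chosen from the outcome data, with a bar against unstructured; under moderate growth in Y-BOCS spread this can modestly understate the week-12 standard error

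*Combined protocol and SAP*

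**What the plan says.** In the combined protocol and SAP, section VI.C (Statistical methods, Primary endpoint), the Y-BOCS model has categorical time (baseline, week 6, week 12), treatment and their interaction. The primary test is the treatment contrast at week 12. Four covariance structures are candidates: AR(1), Toeplitz, compound symmetry and unstructured. The choice is made "based on best fit determined by AIC and BIC", with a further condition: "The unstructured covariance matrix model will only be used if this model fits significantly better than alternative simpler models", judged on -2 log likelihoods.

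The section does not say what happens if AIC and BIC disagree. It names no heterogeneous-variance version of the simpler structures and no robust standard error. The same approach is carried to QIDS-SR, WSAS and Q-LES-Q-SF under the Secondary endpoint. For Exploratory endpoint 2, similar models "will add follow-up assessments (i.e., 3-month and 12-month) to the data as additional time-points".

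The opening of section VI also provides for residual checks and, if needed, transformation to improve normality and homogeneity of variance.

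**The concern.** AR(1), Toeplitz and compound symmetry in standard form share a single variance across visits. If one of them is kept while Y-BOCS scores are more spread out at week 12 than at baseline, the week-12 contrast borrows the smaller early variance and its standard error is too small. The plan makes equal variance the default and leaves it only on a significant test, yet failing to reject equality does not show that it holds.

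The rule is also incomplete. The two criteria penalise parameters very differently, so they will often point to different structures. The structure that produces the primary p-value would then be settled after the outcome data have been seen.

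**Working it through.** **The plan's sample size.** Section VI.D supplies the inputs: 5% two-sided alpha, 90% power, 1:1 randomisation, a week-12 effect of 0.76, an SD of 1.1, and attrition stated as "we assumed a conservative drop-out rate of 20% by end of treatment". The normal approximation is n per arm = 2 × (1.960 + 1.282)² × (1.1/0.76)² = 2 × 10.51 × 2.095 = 44.0, rounded up to 45. The noncentral t gives 46 (power 0.906). Allowing for drop-out, 46/0.80 = 57.5, so 58 per arm and 116 in total, as stated. The sample size is not in question.

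**How strict each gate is.** With three visits, unstructured has 3 × 4/2 = 6 covariance parameters, against 2 for compound symmetry or AR(1) and 3 for Toeplitz. To replace a 2-parameter structure it must lower -2 log likelihood by more than:
- 2 × 4 = 8 under AIC;
- 9.49 under the 5% likelihood-ratio test on 4 df;
- 4 × ln(120) = 19.1 under BIC, if its sample size is taken as the 120 participants.

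So if AIC is followed, the significance test is the binding condition. If BIC is followed, the bar is about twice as high.

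**Size of the effect if equal variance is kept.** Take SDs of 1, 1.15 and 1.3 with 120, 108 and 96 participants observed. The pooled variance is roughly (120 × 1 + 108 × 1.3225 + 96 × 1.69)/324 = 1.312, an SD of 1.145. Against a true week-12 SD of 1.3 the ratio is 0.88, so the standard error would be about 12% too small. Simulation with compound symmetry forced gives 0.870.

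**The rule as written, simulated.** The setting was 120 randomised (section III), 10% missing at week 6 and 20% at week 12, completely at random; REML fits; no treatment effect; 6,000 runs per scenario. Unstructured was used only if it had the lowest AIC (or BIC) and a likelihood-ratio p < 0.05 against every simpler structure. The t reference had week-12 completers minus 2 df. Three inputs are assumptions, not in the documents: correlations of 0.6 (baseline–week 6), 0.7 (week 6–week 12) and 0.5 (baseline–week 12); the SD ratio; and equal SDs in the two arms. Monte Carlo standard error is about 0.3 points.

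| Week-12/baseline SD ratio | Unstructured chosen: AIC / BIC | Model SE ÷ true SE: AIC / BIC / fixed unstructured | Type I error: AIC / BIC / fixed unstructured |
|---|---|---|---|
| 1.0 | 19% / 1% | 0.994 / 0.996 / 0.991 | 4.7% / 4.6% / 4.9% |
| 1.2 | 43% / 6% | 0.956 / 0.918 / 0.992 | 5.9% / 6.9% / 4.9% |
| 1.3 | 71% / 21% | 0.970 / 0.910 / 0.993 | 5.5% / 7.1% / 4.9% |
| 1.4 | 91% / 48% | 0.985 / 0.933 / 0.993 | 5.2% / 6.9% / 4.9% |
| 1.5 | 98% / 75% | 0.992 / 0.963 / 0.994 | 5.1% / 6.2% / 5.0% |
| 2.0 | 100% / 100% | 0.996 / 0.996 / 0.996 | 5.1% / 5.1% / 5.1% |

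A separate simulation of 2,000 runs at ratios 1.2 to 1.3 gave about 5.8% under AIC, 7.0 to 7.7% under BIC and 4.9% for fixed unstructured.

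**Disagreement between criteria.** At a ratio of 1.3, AIC leads to unstructured in 71% of trials and BIC in 21%. The two readings therefore give different primary models in at least 71 − 21 = 50% of trials.

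**Cost of fixing unstructured.** With equal variances and the planned effect (0.76/1.1 = 0.69 SD; 4,000 runs), power is 94.3% for unstructured, 94.2% for compound symmetry and 94.0 to 94.1% for the planned rule.

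**The case against.** The strongest reply is that the harm rests on something the documents do not show. No visit-specific SDs are given. The 10% SD increase in section VI.D is a pandemic allowance on the overall SD, not growth between visits. The eligibility criteria set no minimum Y-BOCS score, so one common cause of growing spread, a truncated baseline range, is absent. This stands, and it makes the point conditional.

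Second, the condition on unstructured is also a safeguard. A reader might infer that the standard error is understated whenever spread grows, or might take the error rates of a forced equal-variance model (7.1% to 13.9% at ratios 1.2 to 2.0) as those of the plan. The documents do not support either reading: unstructured remains a candidate, and at a ratio of 2.0 it was chosen every time with no inflation. Nor should an error rate inferred only from the trials that keep a simpler structure be read as that of the primary test.

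Third, the transformation clause might reduce unequal variance. It is itself a data-dependent step and was not simulated. It could help, but it does not replace a fixed structure.

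Fourth, a reader might object that AR(1) and Toeplitz assume equal spacing. Weeks 0, 6 and 12 are equally spaced, so the primary model is unaffected. The objection reaches only the exploratory follow-up models, where compound symmetry and unstructured do not need equal spacing.

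**Conclusion.** The point holds as a conditional and modest one. Under assumed SD ratios of about 1.2 to 1.5, the week-12 standard error is about 1 to 4% too small if AIC decides and 4 to 9% if BIC decides; type I error is about 5 to 6% or 6 to 7%. Under AIC the excess is visible mainly at ratios 1.2 and 1.3; at 1.4 and 1.5 it lies within simulation error. With equal variances or large growth there is none. Shrinking spread was not simulated, but the same pooling would make the standard error too large and the test conservative.

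Two parts do not depend on how variance behaves: the plan has no rule for AIC and BIC disagreeing, and the restriction on unstructured buys no measurable power at this size. The point therefore merits a change as a free improvement, although it does not invalidate the primary analysis.

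**What to change.** In section VI.C, specify an unstructured covariance matrix in advance for the primary model and the three secondary models. State a fixed fallback for non-convergence only, for example heterogeneous Toeplitz and then heterogeneous compound symmetry. Delete the AIC/BIC choice and the -2 log likelihood condition.

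The cost is two sentences. The sample size of 116 is unchanged and, in the simulations above, no measurable power is lost.

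Naming a small-sample degrees-of-freedom method such as Kenward-Roger is an optional addition; fixed unstructured held 4.9 to 5.1% without it. Applying the same rule to the exploratory follow-up models is a minor consistency point. With five visits unstructured has 5 × 6/2 = 15 parameters, a case these calculations do not cover, so the stated fallback matters more there.

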Smartphone-based CBT for OCD can address gaps in access to treatment, offering standardized, high-quality, empirically-based interventions in a low-cost and accessible format. Additionally, given the low rate of doctoral-level clinicians specializing in CBT for OCD treatment, it would be advantageous to establish whether mobile app-based CBT can be administered effectively with assistance from trained bachelors-level coaches who are supervised weekly by licensed, doctoral-level psychologists. This would greatly enhance scalability of the treatment.

II. SPECIFIC AIMS

The overarching purpose of this project is to test the feasibility, acceptability, and efficacy of mobile-app-delivered CBT for OCD. We accomplish this through Specific and Exploratory Aims 1-3.

Specific Aim 1: In a well-powered, randomized-controlled trial, we will test the efficacy of the active treatment arm (Perspectives OCD) compared to a supportive attentional control (HealthWatch) in reducing primary (i.e., OCD symptom severity, measured via Y-BOCS) and secondary outcomes (e.g., quality of life, depression, social and occupational functioning) at week 12.

Primary Hypothesis: We hypothesize that participants receiving app-based CBT for OCD will have greater improvement in Y-BOCS scores than those in the supportive attentional control condition at treatment endpoint (week 12).

Secondary Hypothesis: We hypothesize that participants receiving app-based CBT for OCD will have greater improvement on secondary clinical outcome measures (i.e., depression (QIDS-SR), functional impairment (WSAS), and quality of life (Q-LES-Q)) than those in the supportive attentional control condition at treatment endpoint (week 12).

Exploratory Aim 2: Feasibility and Acceptability

Hypothesis: We hypothesize that app-delivered CBT for OCD will be feasible (based on drop-out rates) and acceptable (based on descriptive statistics of patient satisfaction, app use, and app feedback as well as qualitative feedback) to individuals with OCD.

Exploratory Aim 3: Maintenance of gains (Y-BOCS, QIDS-SR, Q-LES-Q-SF, WSAS) at follow-up (week 24).

Hypothesis: There will be no significant difference between the primary and secondary outcomes measured at treatment endpoint (week 12) and end of follow-up (week 24) in the group that participated in the app-CBT condition.

III. SUBJECT SELECTION

Overview:

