Baseline differences between the treatment arms in demographic and other potential prognostic variables will be examined using chi-square analyses for discrete variables (if prevalence >10 in the treatment arm with the lower prevalence, or Fisher’s exact test if not) and t-tests for continuous variables. Prior to data analysis, all major variables will be screened for inconsistent or abnormal values. Continuous measures will be assessed for skewness and outliers (based on model residuals), and, if needed, will be transformed to better meet modeling assumptions of normality and homogeneity of variance. A two-tailed p-value $<.05$ will be considered evidence of statistical significance for the primary and secondary outcomes. Our primary and secondary analyses will use generalized linear mixed-effects models (GLMMs). GLMMs can easily accommodate nesting of repeated observations within subjects, include all who complete at least one assessment (including the baseline assessment), and are the preferred method to analyze longitudinal data (Hamer and Simpson, 2009). Despite our best efforts to retain participants, we do expect dropouts (subjects who are lost to follow-up or withdraw early from the study). We will attempt to perform all scheduled assessments for subjects who are withdrawn from the protocol and will provide financial incentives for participation in assessments. Our intent-to-treat sample will include all randomized patients who complete at least one assessment, making our

primary and secondary analyses intent-to-treat analyses. We will also perform “per protocol” analyses. Our per protocol population will include all randomized patients who complete the baseline and post-treatment assessments, and who did not initiate prohibited treatment during the study. We will repeat our GLMM analyses using the per protocol sample. Dropout, study withdrawal, and loss to follow-up will be tabulated by reason and treatment arm. Analyses will be conducted to ascertain to what extent dropouts are nonrandom, and, if so, what factors are associated with dropout. To evaluate potential attrition bias, study dropouts will be compared to study completers.

A. Specific data variables being collected for the study (e.g., data collection sheets)

Specific variables being collected and their timeline are presented above, in Tables 1 and 2, and described in the Study Procedures section.

B. Study endpoints

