Primary endpoint: Difference in OCD severity (Y-BOCS) at the end of treatment (i.e., week 12 assessment).

Hypothesis 1: Participants receiving app-CBT will have lower Y-BOCS scores than those in the supportive attentional control condition at treatment endpoint (week 12).

Secondary endpoints: Difference in secondary clinical outcomes at the end of treatment (i.e., week 12 assessment)

Hypothesis 2: Participants who receive the app-CBT will have better scores on secondary clinical outcome measures than those in the supportive attentional control condition at treatment endpoint (week 12) with respect to:

H2.1: depression severity, as measured by the QIDS-SR, where lower scores are better.

H2.2: functional impairment, as measured by the WSAS, where lower scores are better.

H2.3: quality of life, as measured by the Q-LES-Q-SF, where higher scores are better.

Exploratory endpoint 1: Feasibility and Acceptability

Hypothesis 3.1: Drop-out from app-delivered CBT for OCD will not be higher than drop-out from the supportive attentional control condition, which will indicate feasibility.

Hypothesis 3.2: Patient satisfaction ratings (i.e., CSQ total scores) in the group receiving app-delivered CBT for OCD will not be lower than those in the supportive attentional control condition, which will indicate acceptability.

Hypothesis 3.3: App-delivered CBT for OCD will be acceptable to individuals with OCD based on descriptive statistics of app use, app feedback, and qualitative feedback comments.

Exploratory endpoint 2: Maintenance of gains (Y-BOCS, QIDS-SR, WSAS, Q-LES-Q-SF) during follow-up (at 3-month and 12-month follow-up assessments).

Hypothesis 4: At the 12-month follow-up assessment, participants who received app-CBT will have lower Y-BOCS scores than those in the supportive attentional control condition.

Exploratory endpoint 3: Treatment utilization for OCD concerns following the 3-month follow-up.

Hypothesis 5: Participants assigned to the app-CBT treatment condition will be less likely to seek additional treatment for OCD than participants assigned to the supportive attentional control condition prior to the 12-month follow-up assessment.

C. Statistical methods

For all statistical analyses, we will use a Type I error probability of 0.05 to determine significance unless otherwise noted.

Primary endpoint: Difference in OCD severity (Y-BOCS) at the end of treatment (i.e., preliminary efficacy for primary OCD symptoms)

Analysis:

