We will use the same hierarchical mixed modeling approach as described for the primary endpoint to examine significant differences in secondary outcome measures (i.e., depression severity (H2.1), functional impairment (H2.2), and quality of life (H2.3)) at post-treatment between participant in the app-CBT vs. supportive attentional control conditions. We will not adjust for multiple testing among secondary outcomes based on the recommendation of Cook and Farewell (1996), who argue that multiplicity adjustments are not necessary if separate test results are interpreted marginally and address different aspects of the patient experience and decision-making process rather than alternative assessments of efficacy.

Exploratory endpoint 1: Assess feasibility and acceptability

Analysis:

We will test feasibility and acceptability by examining:

- H3.1: Refusal and dropout rates and reasons, by group: Drop-out rates by treatment (app-CBT vs. supportive attentional control) will be compared using logistic regression. Drop-outs will be defined operationally as participants who do not complete either an endpoint or follow-up assessment of the primary outcome measures (Y-BOCS), as well as participants in the CBT arm who do not use the app or participants in the HealthWatch arm who do not use the website at least once between assessments (i.e., at least once between baseline and week 6 and at least once between week 6 and week 12). We will use one-tailed tests to examine if the odds of drop-out in the app-CBT group are higher; if non-significant, we will interpret the results as an indication that the app-CBT treatment is feasible in comparison to the supportive attentional control condition; conversely, significantly higher odds of drop-out in the app-CBT condition would indicate a lack of feasibility.

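### The primary week-12 Y-BOCS contrast gives each arm its own baseline mean, so the baseline score already collected does little to sharpen the treatment estimate

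*Combined protocol and SAP*

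**What the plan says.** Section VI.C (Primary endpoint, Analysis) treats baseline as one of three levels of a categorical time factor. The fixed effects are time, treatment and their interaction. The covariance is AR(1), Toeplitz, compound symmetry or unstructured, chosen by fit. Then: "The main hypothesis test will be based on a specific contrast of treatment difference at week 12". No section names a baseline covariate or requires the arms to share a baseline mean.

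Other places that bear on this:

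- Section VI.B defines the primary endpoint as "Difference in OCD severity (Y-BOCS) at the end of treatment (i.e., week 12 assessment"), and its Hypothesis 1 is worded as lower scores at week 12. Both match the test.
- Section II (Primary Hypothesis) says app participants "will have greater improvement in Y-BOCS scores than those in the supportive attentional control condition", which is the language of change.
- The opening of Section VI says "Baseline differences between the treatment arms in demographic and other potential prognostic variables will be examined", but not what a difference would mean for the primary estimate. It also says the models "include all who complete at least one assessment (including the baseline assessment").
- For the secondary outcomes, Section VI.C says "We will use the same hierarchical mixed modeling approach as described for the primary endpoint".
- Section VI.D sizes the trial on "an assumption of an effect size of 0.76 comparing the two treatments at the end of treatment", with SD 1.1, and adds "we assumed a conservative drop-out rate of 20% by end of treatment".

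**The concern.** Having baseline in a mixed model is easily taken to mean that the treatment effect is adjusted for it. Here it is not. The mean structure is saturated (three visits by two arms, six free means), so a chance difference between arms at baseline is fitted as such and does not correct the week-12 difference.

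Baseline severity is a natural predictor of week-12 severity, and the trial already measures it. Randomisation is stratified only by medication status, so the design does not balance severity either. What is at stake is precision: a wider confidence interval than necessary, and less reserve if the true effect falls below 0.76. Section VI.D itself cites trials with effects of 0.55 and 0.52. Taking out chance imbalance and narrowing the interval are one gain seen from two sides and should not be counted twice.

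**Working it through.** **1. The plan's own figure.** Inputs from Section VI.D: difference 0.76, SD 1.1, two-sided alpha 0.05, power 0.90, dropout 20%. A two-sample t calculation needs 46 completers per arm (power 90.6%). 46/0.80 = 57.5, rounded up to 58 per arm, or 116. The stated size is reproduced with no credit for baseline.

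**2. Complete data, 60 per arm (the randomisation target of 120).** Let rho be the correlation of baseline with week 12.

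- Planned contrast: variance = 2 × 1.1² / 60 = 0.0403, SE 0.2008 at every rho.
- Common baseline mean: variance × (1 − rho²).
- Difference in change: variance × 2(1 − rho).

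| rho | Planned SE | Common-baseline SE | Change-score SE |
|---|---|---|---|
| 0.3 | 0.2008 | 0.1916 | 0.2376 |
| 0.5 | 0.2008 | 0.1739 | 0.2008 |
| 0.7 | 0.2008 | 0.1434 | 0.1556 |

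**3. With 20% missing at week 12.** The documents give neither correlations nor dropout timing. Assumptions, per arm: 48 complete, 6 lost after week 6, 6 lost after baseline; week 6 to week 12 correlation 0.7; baseline correlated rho with both later visits. Variances come from the generalised least squares information matrix, with free or common baseline means.

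| rho | Planned SE | Common-baseline SE | Variance ratio | Variance cut |
|---|---|---|---|---|
| 0.3 | 0.2173 | 0.2088 | 0.923 | 8% |
| 0.4 | 0.2165 | 0.2010 | 0.862 | 14% |
| 0.5 | 0.2154 | 0.1905 | 0.783 | 22% |
| 0.6 | 0.2140 | 0.1768 | 0.683 | 32% |
| 0.7 | 0.2121 | 0.1588 | 0.561 | 44% |

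Completers alone would give SE 1.1 × √(2/48) = 0.2245. So the planned model does recover something for dropouts: 1 − (0.2173/0.2245)² = 6% of the variance at rho 0.3, and 1 − (0.2121/0.2245)² = 11% at rho 0.7.

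**4. Equivalent sample size.** 120/0.923 = 130, 120/0.783 = 153, 120/0.561 = 214 randomised for the planned contrast to match the adjusted one at rho 0.3, 0.5 and 0.7.

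**5. Power**, normal approximation Φ(difference/SE − 1.96), planned → common baseline:

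| True difference | rho 0.3 | rho 0.5 | rho 0.7 |
|---|---|---|---|
| 0.76 | 93.8% → 95.4% | 94.2% → 97.9% | 94.8% → 99.8% |
| 0.605 (0.55 SD) | 79.5% → 82.6% | 80.2% → 88.8% | 81.4% → 96.8% |
| 0.55 (0.50 SD) | 71.6% → 75.0% | 72.4% → 82.3% | 73.7% → 93.4% |

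**6. Sensitivity.** With the week 6 to week 12 correlation from 0.5 to 0.8, and dropout all before week 6, split, or all after it, the cut stays at 7–8% (rho 0.3), 21–23% (rho 0.5) and 43–45% (rho 0.7).

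**7. Chance imbalance, complete data.** The SE of the baseline difference in SD units is √(2/60) = 0.183, so a difference of at least 0.25 SD in either direction has probability 17%, about half of it against the app. In simulation, the planned contrast's power for 0.76 in those unfavourable trials is 90%, 84% or 76% (rho 0.3, 0.5, 0.7), against 96% over all trials. It is 99% or more when the imbalance favours the app. These figures show where the lost precision falls; they are not an extra loss.

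**The case against.** The main objection is about weight. The planned test is valid, matches the endpoint in Section VI.B, and by the figures above already has 94–95% power at the design effect. Adjustment adds about 2 to 5 points there. That is right, and it is why this is offered as an improvement and not as a fault.

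Second, the size depends on a correlation the documents do not give, and it can be smaller than the range shown. Under AR(1), one of the listed structures, the baseline to week-12 correlation is the square of the adjacent-visit one. With adjacent correlations of 0.4, 0.5, 0.6 and 0.7 (0.16, 0.25, 0.36 and 0.49 from baseline to week 12), the variance cut is 2%, 5%, 11% and 21%. This stands as a lower end. Adjustment still gained at every value tried.

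Third, it is not fully clear which score is the baseline. The screening section lets some participants reuse assessments from another study done up to six months earlier, and the note to the Measures Chart has Y-BOCS repeated when more than ten days pass before treatment starts. A common baseline mean is justified only for a score taken before randomisation. The planned model has the same ambiguity, and naming the score settles it.

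Fourth, if the change wording in Section II governed, the complete-data saving would be (1 − rho)/2, that is 35%, 25% and 15% at rho 0.3, 0.5 and 0.7. The size would differ, but the direction would not.

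**Conclusion.** The point holds as a missed gain in efficiency. As written, the primary contrast takes nothing from baseline when data are complete and only a little when they are not. A common baseline mean would cut its variance by about 8% to 44% for assumed baseline correlations of 0.3 to 0.7, and by less if the correlation is lower. The algebra is certain; the size rests on correlations and dropout timing that the documents do not give. The sample size, type I error and stated power are not undermined. The practical benefit is a narrower interval and more reserve at effects below 0.76. The same change is open for the three secondary outcomes, where the gain has not been quantified.

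**What to change.** In Section VI.C (Primary endpoint), keep the three-visit mixed model but constrain the arms to a common baseline mean, with treatment effects at week 6 and week 12 only, and test the baseline-adjusted week-12 difference. This keeps participants who have only a baseline score, as the opening of Section VI requires. The alternative is to model weeks 6 and 12 as outcomes, with baseline Y-BOCS and its interaction with time as covariates; that form drops baseline-only participants.

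Also:

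- State which pre-randomisation Y-BOCS is the baseline when there is more than one.
- Use the same form for QIDS-SR, WSAS and Q-LES-Q-SF.
- Word the hypotheses in Sections II and VI.B alike.
- Fix this before unblinded data are seen, so that adjustment does not depend on the planned baseline comparisons.

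Do not move to a plain change-score contrast: with complete data it is less precise than the planned test when rho is below 0.5 (SE 0.238 against 0.201 at rho 0.3).

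The cost is a few words in the analysis section. It needs no new data or patients and no change to the sample size.
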